9.6.12 Asthma Control Test™

In patients with comorbid asthma, the ACT (Appendix 8 [Section 19.8](#)) will be completed by patients at Screening; pre-dose on Days 0, 21, and 49; and on Days 84, and 112 or ET to assess the frequency of shortness of breath and general asthma symptoms, use of asthma rescue medications, the effect of asthma on daily functioning, and overall asthma control.

9.6.13 Exploratory Biomarkers

Blood samples (5 mL serum, 5 mL plasma, and 5 mL RNAlater solution) will be obtained on Day -3, pre-dose on Days 21 and 49, and on Day 84 and stored for potential analyses of markers of MCs and eosinophils and of inflammatory response in blood. In the event that a patient does not provide consent for future analyses or storage of these samples, they will be destroyed according to the country-specific ICF.

Specific details of sampling and sample storage and processing procedures will be documented in a separate manual to be filed in the trial master file. The results of the analyses will be reported in an appendix to the clinical study report.

10 EVALUATIONS BY VISIT

Evaluations and procedures by visit are depicted in [Table 1](#).

11 ADVERSE EVENT REPORTING AND DOCUMENTATION

11.1 Adverse Events

In accordance with 21 Code of Federal Regulations (CFR) 312.32(b), an AE is any untoward medical occurrence in a clinical investigation of a patient administered a pharmaceutical product and that does not necessarily have a causal relationship with the treatment. An AE is therefore any unfavorable and unintended sign (including an abnormal laboratory finding), symptom, or disease temporally associated with the administration of an investigational product, whether or not related to that investigational product. An unexpected AE is one of a type not identified in nature, severity, or frequency in the current IB or of greater severity or frequency than expected based on the information in the IB.

AE Recording:

At each evaluation, the Investigator will determine whether any AEs have occurred. The assessment of an AE will be done pursuant to definitions set forth by International Conference on Harmonisation (ICH)/Good Clinical Practice (GCP) Guidelines and other applicable regulatory requirements. The patient will be questioned in a general manner and no specific symptoms will be suggested (e.g., ask the patient if he/she has had have had any “changes in health” since the last visit or assessment).

The Investigator or designee will be notified if any patient experiences an AE. Any initial information discovered by the Investigator or designee (i.e., complaint[s] and known start/end dates and times) will be documented on the patient’s AE form. The Investigator or

designee will assess the initial AE finding(s) to determine if the medical occurrence is in fact an AE by officially documenting the condition/diagnosis on the AE form.

In the event that the Investigator is not available, the assigned staff will page the Sub-investigator on-call and have the AE documented by telephone contact. The medication dispensed will be documented on an Investigator order form, and the phone call will be documented on the same form (if applicable). The patient will be seen by the Investigator as soon as possible.

Action taken will be categorized as “none,” “study drug discontinued,” “dose modified,” “required concomitant medication,” “required procedure,” or “other.”

Event outcome at resolution or time of last follow-up will be recorded as “recovered,” “recovering,” “not recovered,” “recovered with sequelae,” “fatal,” or “unknown.”

AE Severity:

Adverse events are to be recorded on the AE page of the eCRF. Severity will be graded according to the definitions, based on the Common Terminology Criteria for Adverse Events, Version 4.0,⁷ listed in [Table 2](#). It should be pointed out that the term “severe” is a measure of intensity and that a severe AE is not necessarily serious.

When the intensity of an AE changes more than once a day, the maximum severity for the event should be listed. If the intensity changes over a number of days, these changes should be recorded separately (i.e., having distinct onset dates).

Table 2 Adverse Event Severity Grading

Grade	Severity	Description
1	Mild	Transient or mild discomfort; no limitation in activity; no medical intervention or therapy required. The patient may be aware of the sign or symptom but tolerates it reasonably well.
2	Moderate	Mild to moderate limitation in activity, no or minimal medical intervention/therapy required.
3	Severe	Marked limitation in activity, medical intervention/therapy required, hospitalizations possible.
4	Life-threatening	The patient is at risk of death due to the adverse experience as it occurred. This does not refer to an experience that hypothetically might have caused death if it were more severe.
5	Death	Any adverse event for which the outcome is death.

Adverse Event Relationship to Study Drug:

The relationship of an AE to the study drug should be assessed using the following the guidelines in [Table 3](#).

Table 3 Adverse Event Relationship to Study Drug

Relationship to Drug	Comment
Related	There is clear evidence that the event is related to the use of study drug (e.g., confirmation by positive re-challenge test).
Possible	The event cannot be explained by the patient's medical condition, concomitant therapy, or other causes, and there is a plausible temporal relationship between the event and study drug administration.
Unlikely/Remote	An event for which an alternative explanation is more likely (e.g., concomitant medications or ongoing medical conditions) or the temporal relationship to study drug administration and/or exposure suggests that a causal relationship is unlikely. (For reporting purposes, "Unlikely/Remote" will be grouped together with "Not Related.")
Not Related	The event can be readily explained by the patient's underlying medical condition, concomitant therapy, or other causes, and, therefore, the Investigator believes no relationship exists between the event and study drug.

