14.3 Study Stopping Rules

The trial must be discontinued prematurely in the event of any of the following:

- A life-threatening adverse event that is possibly or probably related to treatment
- A fatal adverse event that is possibly or probably related to treatment
- New information leading to unfavorable risk-benefit judgment of the study drug, e.g., occurrence of significant previously unknown adverse reactions, unexpectedly high intensity or incidence of known adverse reactions, or other unfavorable safety findings
- >25% of patients at any time have been withdrawn due to drug-related AEs, including those related to abnormal laboratory results, or other safety findings
- Sponsor's decision that continuation of the trial is unjustifiable for medical or ethical reasons
- Poor enrollment of patients making completion of the trial within an acceptable time frame unlikely
- Discontinuation of development of the Sponsor's study drug

Regulatory Authorities and IRBs/IECs will be informed about the discontinuation of the trial in accordance with applicable regulations. The trial may be terminated or suspended upon request of Regulatory Authorities.

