15.6 Safety Analysis

Safety and tolerability will be assessed throughout the study by monitoring and evaluating TEAEs, including any complications resulting from the IV infusion, and changes in vital signs and in clinical safety laboratory test (including ADA) and PE findings. All safety and tolerability endpoints will be summarized by treatment. Baseline for all safety endpoints will be defined as the last recorded observation before the administration of the IV infusion of study drug. Safety measures, including AEs, clinical safety laboratory tests (including ADA), vital signs, PEs, and concomitant medication usage, will be summarized descriptively. For quantitative variables, descriptive statistics, including number of observations, means, medians, SDs, and ranges, will be provided for the values themselves as well as for the changes from Baseline by treatment group at each study visit. Qualitative variables will be summarized using counts and percentages in each treatment group at each study visit.

Adverse Events:

All AEs will be coded using the latest version of the Medical Dictionary for Regulatory Activities (MedDRA) and will be classified by MedDRA system organ class (SOC) and preferred term. The summaries of AEs will be based on TEAEs. A TEAE is defined as an AE reported in the clinical database with a date of onset (or worsening) on or after the start date of study drug through the end of the study.

The following information will be presented for AEs:

- TEAEs by SOC and preferred term
- TEAEs by maximum severity, SOC, and preferred term
- Drug-related TEAEs by SOC and preferred term
- TEAEs leading to withdrawal by SOC and preferred term
- Serious TEAEs by SOC and preferred term

All AEs will be collected starting from the first study drug administration through Day 168 or ET. Severity will be assessed by the Investigator using the protocol-defined grading scales (Section 11.1). All AEs will also be judged by the Investigator as to whether they are clinically significant and related to study drug.

Vital Signs:

Body temperature, supine systolic and diastolic blood pressure, pulse, and respiratory rate will be measured at Screening and on Days -3, 0, 14, 21, 49, 84, 112, and 168 or ET. On Days 0, 21, and 49, vital signs will be measured pre-dose, every 15 minutes after the start of infusion, and immediately following the end of infusion. All vital signs will be measured after the patient has been in the supine position for ≥ 5 minutes.

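### Table 3 has no drug-related grade for an adverse event with plausible timing that either the study drug or another cause could explain

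*Protocol*

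**What the plan says.** Protocol Section 11.1, Table 3 defines four causality grades:

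- **Related**: "There is clear evidence that the event is related to the use of study drug", with a positive re-challenge as the example.
- **Possible**: two conditions joined by *and*. The first is "The event cannot be explained by the patient's medical condition, concomitant therapy, or other causes"; the second is "and there is a plausible temporal relationship between the event and study drug administration".
- **Unlikely/Remote**: "An event for which an alternative explanation is more likely", or timing that speaks against the drug. For reporting, this grade "will be grouped together with" Not Related.
- **Not Related**: another cause readily accounts for the event, and for that reason the investigator sees no link with the drug.

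The grade is used in two later places. Section 14.3 requires the trial to be discontinued after a single life-threatening or fatal event judged possibly or probably related, and when more than 25% of "patients at any time have been withdrawn due to drug-related AEs" or on the related grounds listed there. Section 15.6 lists "Drug-related TEAEs by SOC and preferred term" among the adverse event summaries.

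**The concern.** A causality scale should have a place for the confounded event: the timing fits the drug, and another cause fits too. In Table 3 the middle grade is labelled Possible but is defined by exclusion of every other cause.

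Confounded events will not be rare in this trial. At least 50% of patients are to have comorbid asthma (at least 0.50 × 70 = 35 of about 70), all use a common nasal steroid, and asthma medications are allowed. For a respiratory event after an infusion, asthma is a ready candidate in at least half of the patients. The earlier clinical experience described is one single-dose Phase 1 study with 26 subjects on AK001, whereas this trial gives three infusions, so causality judgements carry weight.

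At stake are the drug-related TEAE table and the stopping rules that depend on the grade. Sites apply the definitions when they record the event, so a statistical analysis plan cannot later restore a grade that the wording did not offer.

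**Working it through.** The protocol states no count or rate of drug-related events, so there is no figure to reproduce. The check is a reading of the four definitions against each other, followed by an illustration with assumed inputs.

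**Step 1. Test the grades on an event with plausible timing and a plausible alternative cause.**

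| Grade | Does the event qualify? | Counted as |
|---|---|---|
| Related | No: there is no clear evidence | drug-related |
| Possible | No: the event can be explained otherwise | drug-related |
| Unlikely/Remote | Only if the alternative is more likely than the drug | not related |
| Not Related | Only if the alternative readily explains it and the investigator sees no link | not related |

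If drug and alternative are about equally plausible, none of the four rows is met.

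**Step 2. Direction of the error.** An investigator faced with such an event can pick one of the two lower grades, in which case it leaves the drug-related count, or can depart from the wording and choose Possible, in which case nothing is lost. No route adds an event. The effect is zero or downward.

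**Step 3. Match with the rules that use the grade.** Section 14.3 speaks of a possible or probable relationship for its single-event rules, but Table 3 has no Probable grade. Sections 14.3 (withdrawals) and 15.6 speak of drug-related events without saying which grades count. Aligning these terms alone would not close the gap, because the exclusion sits inside the definition of Possible.

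**Step 4. Illustration for the 25% withdrawal rule.** Inputs: N = 70 (Section 15.7) and a threshold of more than 25%. Since 0.25 × 70 = 17.5, the rule fires at 18 patients. Assumed, and not in the protocol: p, the true proportion of all patients withdrawn for drug-linked events; q, the share of those graded outside Possible and Related; independence between patients; and the full 70 as denominator. The chance that the rule fires is P(X ≥ 18) with X ~ Binomial(70, p(1 − q)). For example, p = 0.30 and q = 0.25 give 0.30 × 0.75 = 0.225 and a probability of 0.301.

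| p | q = 0 | q = 0.10 | q = 0.25 | q = 0.50 |
|---|---|---|---|---|
| 0.30 | 0.819 | 0.640 | 0.301 | 0.014 |
| 0.40 | 0.996 | 0.975 | 0.819 | 0.148 |

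The expected counted proportion falls to the 25% line when q = 1 − 0.25/p: 1 − 0.25/0.30 = 0.167 at p = 0.30, and 1 − 0.25/0.40 = 0.375 at p = 0.40. For the single-event rules, the chance that one drug-linked event does not trigger the rule is q itself.

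These rates of p are high: 0.30 × 70 = 21 withdrawals, while no Phase 1 subject was discontinued for an adverse event. The table shows how sensitive the rule is to q. It forecasts nothing.

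**The case against.** The strongest reply has three parts.

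**The text does not order a downgrade.** A reader might infer that Table 3 sends every confounded event to Not Related. It does not. Not Related also needs the investigator to see no link with the drug, which does not fit someone who finds the drug plausible, and Unlikely/Remote needs an alternative that is more likely, not merely available. Table 3 is also introduced as guidance, and Section 11.3.1 asks investigators for their opinion on causality. An experienced investigator may well choose Possible despite the wording. This stands: the defect is a gap, and under-counting is its consequence only where sites follow the wording.

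**Much of the safety system does not use the grade.** Section 15.6 also tabulates all TEAEs, TEAEs by maximum severity, serious TEAEs and those leading to withdrawal, in a blinded placebo-controlled comparison. SAEs are reported within 24 hours whatever the cause, individual withdrawal does not depend on causality, any safety concern puts enrollment on hold, the DMC reviews safety and can ask for treatment identities, and Section 14.3 has a separate clause on unfavorable risk-benefit information. This also stands. A reader might infer a falsely clean safety profile or a late stop overall; the documents do not support that. These safeguards limit the harm but leave the causality-dependent rules and table as they are.

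**The size cannot be derived.** A reader might want to attach a percentage to the lost events, or argue from atopy in this population. The protocol gives neither a share of confounded events nor a share of atopic patients. Only the asthma minimum is documented, and it does not say how many events are affected.

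**Conclusion.** The point holds as a gap in the scale. Table 3 has no drug-related grade for an event with plausible timing that either the study drug or another cause could explain. Applied as written, it can only lower the count in the drug-related TEAE table and in the life-threatening, fatal and 25% withdrawal rules of Section 14.3.

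The size is unknown. It depends on how many drug-linked events have a competing explanation and on how literally sites read Possible; the protocol informs neither. The conclusion about direction needs no numerical assumption. The probabilities for the 25% rule rest entirely on assumed p and q.

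The effect is confined to outputs that use the grade. Because grading is blinded, the same wording applies in all arms, and the all-causality comparison with placebo is untouched. The change is worth making because it is small and because it acts at data capture, where a later analysis plan cannot help.

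**What to change.** Reword Possible in Table 3 along these lines: the temporal relationship is plausible and the study drug cannot be excluded as a cause, even though the medical condition, concomitant therapy or another cause could also explain the event.

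Leave Unlikely/Remote and Not Related as they are. Restricting Not Related to events with a proven other cause would be a preference and is not needed to close the gap.

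Reconcile Table 3 with Sections 14.3 and 15.6, so that the causality terms there correspond to grades that exist and it is stated which grades count as drug-related. This point takes no view on the stopping thresholds themselves.

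The cost is the wording of one table, the eCRF completion guidance and site training. The downside should be accepted openly: somewhat more events will count as drug-related in every arm, including placebo, and the causality-dependent rules in Section 14.3 become easier to meet. Since one possibly related life-threatening or fatal event obliges the sponsor to discontinue the trial, the sponsor should review the new wording together with those rules.

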11.2 Serious Adverse Events

An SAE is defined as any AE occurring at any dose that results in any of the following outcomes:

- Death
- A life-threatening AE; the patient is at risk of death at the time of the event. It does not refer to an event that hypothetically might cause death if it were more severe.
- Inpatient hospitalization or prolongation of existing hospitalization
- A persistent or significant disability/incapacity
- A congenital anomaly/birth defect

Other important medical events may also be considered an SAE when, based on appropriate medical judgment, they jeopardize the patient or require intervention to prevent one of the outcomes listed.

Note:

Medical and scientific judgment should be exercised in deciding whether SAE reporting is also appropriate in situations other than those listed above. For example, important medical events may not be immediately life-threatening or result in death or hospitalization but may jeopardize the patient or require intervention to prevent 1 of the outcomes listed in the definition above (including suspected transmission of an infectious agent by a medicinal product should be reported as an SAE). Any AE is considered an SAE if it is associated with clinical signs or symptoms judged by the Investigator to have a significant clinical impact.

11.3 Procedures

11.3.1 All Adverse Events

In the event that a patient completes a study with an ongoing AE, investigational site personnel will continue to follow-up with the patient until AE resolution is reached and documented. If, after 30 days from the study completion date, the AE is still continuing but not assessed as serious, the outcome will be recorded as “not recovered,” and no further follow-up will be necessary.

All AEs identified will be recorded in the eCRF from the time of study drug administration until completion of the last study-related procedure (Day 168 or ET). All SAEs will be reported from the time the patient signs an ICF until completion of the last study-related procedure (Day 168 or ET).

All AEs, regardless of seriousness, severity, or presumed relationship to investigational product, must be recorded using medical terminology in the source document and the eCRF. Whenever possible, diagnoses should be given when signs and symptoms are due to a common etiology (e.g., dysuria and urinary nitrites should be reported as a urinary tract infection). Investigators must record their opinions concerning the relationship of the AE to the investigational product in the eCRF.

Patients (or their designees, if appropriate) may be provided with a “study card” indicating the name of the investigational product, the study number, the Investigator’s name, a 24-hour emergency contact number, and, if applicable, excluded concomitant medications.

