2 RATIONALE FOR STUDY AND DOSE SELECTION

The present study is a Phase 2, randomized, double-blind, placebo-controlled study of the safety and tolerability of 2 different dose levels of AK001 compared with placebo in patients with moderate to severe chronic nasal polyposis and whose symptoms are resistant to treatment with INs.

In Study AK001-001, dose-related pharmacokinetic (PK) parameters, including maximum plasma concentration (C_{max}), area under the plasma concentration-time curve from zero hours to time (t) ($AUC_{[0-t]}$), and area under the plasma concentration-time curve from zero hours to infinity ($AUC_{[inf]}$), increased in a dose-proportional manner. The geometric mean (gMean) terminal elimination half-life ($t_{1/2}$) was in the range of 20 to 27 days, which is typical for a MAb. The gMean clearance ranged from 4.85 to 6.86 mL/hour and did not appear to be a function of body weight or body mass index (BMI). The gMean volume of distribution (V_z) was 0.060 L/kg, also typical for a MAb.

Siglec-8 internalization was durable and persisted as long as AK001 was present in serum. Siglec-8 internalization was not observed at Day 28 in the lowest dose cohort, 0.01 mg/kg, consistent with the undetectable levels of serum AK001 at Day 28. In all other dose cohorts, Siglec-8 internalization was maintained through Day 28.

The recommended Phase 2 doses of 25 mg and 250 mg administered IV every 3 to 4 weeks were calculated on the basis of nonclinical PK and pharmacodynamic data and on the PK and safety data collected in the Phase 1 study. These doses are expected to maintain 60% to 80% engagement and internalization of the Siglec-8 receptor; 60% to 80% internalization of the Siglec-8 receptor is associated with substantial inhibition of MCs and killing of activated eosinophils in in vitro experiments.

For additional information, please see the Investigator's Brochure (IB).

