12 DISCONTINUATION AND REPLACEMENT OF PATIENTS

12.1 Early Discontinuation of Study Drug

A patient may be discontinued from study treatment at any time if the patient, the Investigator, or the Sponsor feels that it is not in the patient's best interest to continue. The following is a list of possible reasons for study treatment discontinuation:

- Patient's withdrawal of consent
- Patient is not compliant with study procedures
- AE that, in the opinion of the Investigator, results in it being in the best interest of the patient to discontinue study treatment
- Protocol violation requiring discontinuation of study treatment
- Loss to follow-up
- Sponsor's request for ET of study
- Positive pregnancy test (females)

If a patient is withdrawn from treatment due to an AE, the patient will be followed and treated by the Investigator until the abnormal parameter or symptom has resolved or stabilized.

All patients who discontinue study treatment should come in for an ET visit as soon as possible.

All patients are free to withdraw from participation at any time for any reason, specified or unspecified, and without prejudice.

Reasonable attempts will be made by the Investigator to provide a reason for patient withdrawals. The reason for the patient's withdrawal from the study will be specified in the patient's source documents. Refer to [Table 1](#) for ET procedures.

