12.2 Withdrawal of Patients from the Study

Participation of a patient will be discontinued in the event that:

- An AE or SAE that, in the judgment of the Investigator, requires treatment withdrawal due to its nature, severity, or required treatment, regardless of the causal relationship to treatment
- Protocol violations, including non-compliance, loss to follow-up

- Occurrence of an exclusion criterion that is clinically relevant and affects the patient's safety, if discontinuation is considered necessary by the Investigator and/or Sponsor
- Serum transaminases (ALT and/or AST) $>3 \times$ upper limit of normal (ULN) AND total bilirubin $>2 \times$ ULN (confirmed by subsequent repeat) without an alternative explanation
- Elevation of ALT or AST $>3 \times$ ULN (confirmed by repeat) with the appearance or worsening of symptoms felt by the Investigator to be potentially related to hepatic inflammation, such as fatigue, nausea, vomiting, right upper quadrant pain or tenderness, fever, rash, or eosinophilia
- Use of a non-permitted concomitant drug, as defined in [Section 7.1](#)
- Withdrawal of the patient's consent
- Participation in any other trial during the duration of this trial
- Loss of ability to freely provide consent through imprisonment or involuntary incarceration for treatment of either a psychiatric or physical (e.g., infectious disease) illness
- Discretion of the Investigator

All patients are free to withdraw from participation at any time for any reason specified or unspecified, and without prejudice.

Reasonable attempts will be made by the Investigator to provide a reason for patient withdrawals. The reason for the patient's withdrawal from the study will be specified in the patient's source documents. As noted above, patients who discontinue study treatment early (i.e., they withdraw prior to Day 168) should have an ET visit. Refer to [Table 1](#) for ET procedures. Patients who withdraw after Day 84 but prior to Day 168 should be encouraged to come in for a final visit.

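### New adverse events, including serious ones, are not collected after an early termination visit, although the protocol plans 17 weeks of observation after the last dose

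*Protocol*

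**What the plan says.** Three rules of the protocol combine.

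- **Collection window.** Section 11.3.1 records AEs "from the time of study drug administration until completion of the last study-related procedure (Day 168 or ET"). The same section says of serious events: "All SAEs will be reported from the time the patient signs an ICF until completion of the last study-related procedure (Day 168 or ET"). Section 9.2.8 gives the same end point for both, and 15.6 repeats it for AEs: "All AEs will be collected starting from the first study drug administration through Day 168 or ET".
- **Timing of ET.** Section 12.1: "All patients who discontinue study treatment should come in for an ET visit as soon as possible". The listed reasons for stopping include an "AE that, in the opinion of the Investigator, results in it being in the best interest of the patient to discontinue study treatment".
- **Status after stopping.** Section 12.2 equates stopping drug with leaving the study: "patients who discontinue study treatment early (i.e., they withdraw prior to Day 168) should have an ET visit". The protocol does not keep such patients on the Day 84, 112 and 168 visits for safety.

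The planned safety observation is longer. Section 4.1 sets a 17-week post-treatment period. Inclusion criteria 9 and 10 describe 17 weeks after the last dose as about five half-lives. Section 2 says the half-life "was in the range of 20 to 27 days, which is typical for a MAb".

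**The concern.** Stopping study drug and ending safety collection are different things, but the protocol ties them together. A completer is watched for AEs through the whole period in which the antibody is cleared. A patient who stops early is dismissed from new-event collection at a visit that should happen promptly, while much of the antibody is still present.

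Section 5.1 lists treatment-emergent AEs (TEAEs) first among the primary safety endpoints. Section 15.6 tabulates them by preferred term, by maximum severity and by seriousness, over all dosed patients. A delayed reaction starting after ET would appear in none of these tables. Section 14.3 also requires the trial to stop for a single life-threatening or fatal event judged at least possibly related. If such an event began after ET, it would fall outside the window in which sites are told to report SAEs.

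**Working it through.** **1. The protocol's own figure.** The last infusion is on Day 49 and the final visit on Day 168.

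- 168 − 49 = 119 days = 17 weeks.
- In half-lives: 119/27 = 4.4 to 119/20 = 5.95, and exactly 5 at 119/5 = 23.8 days.

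The statement that 17 weeks is about five half-lives therefore reproduces.

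**2. What is followed after ET.** The provisions are:

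- 12.1, patients withdrawn because of an AE: "the patient will be followed and treated by the Investigator until the abnormal parameter or symptom has resolved or stabilized". This covers the event that led to withdrawal.
- 11.3.1: AEs ongoing at study completion are followed until resolution; a non-serious one still continuing after 30 days is closed as not recovered.
- 11.3.2: SAEs unresolved at the end of participation are followed until one of five listed conditions is met.

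Each applies to an event already present. None asks about new events after ET.

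**3. Drug remaining at ET.** Example (assumed timing): one infusion on Day 0, ET on Day 14, first-order decay at the terminal half-life.

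- Fraction remaining = 0.5^(14/half-life).
- Half-life 20 days: 0.5^(14/20) = 0.62. Half-life 27 days: 0.5^(14/27) = 0.70.
- Observation lost to Day 168: 168 − 14 = 154 days. Of the 119 days that a completer has after the last dose, this patient has 14.

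For a completer at 119 days, the remaining fraction is 0.5^(119/20) = 1.6% to 0.5^(119/27) = 4.7%.

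**4. Share of an arm's observation lost.** The protocol gives no early-stop rate. Assume a fraction f of an arm stops, between 5% and 25%. The upper end is the threshold in 14.3 for withdrawals due to drug-related AEs.

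- ET at Day 14: f × 154/168 = 4.6% (f = 5%) to 22.9% (f = 25%) of planned patient-days.
- ET at Day 28: f × 140/168 = 4.2% to 20.8%.
- If f is near zero, the loss is near zero.

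**The case against.** A reader might infer that the shortened record makes the worse-tolerated arm look safer in the overall TEAE percentage. The documents do not support that.

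A dosed patient who stops because of an AE has, by the definition in 15.6, already had a TEAE and is counted. Suppose the true risk of any TEAE is 40% in both arms, and 20% of an active arm but 5% of placebo stop because of an AE (all assumed):

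- Active: stayers' risk is (40 − 20)/80 = 25%, so recorded 0.20 × 100% + 0.80 × 25% = 40%.
- Placebo: stayers' risk is (40 − 5)/95 = 36.8%, so recorded 0.05 × 100% + 0.95 × 36.8% = 40%.

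There is no distortion in that row. If stayers instead keep a 40% risk, the recorded figures are 52% and 43%, and the worse-tolerated arm looks worse.

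Other points also limit the concern:

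- AE withdrawals are themselves a primary safety endpoint (5.1), and TEAEs leading to withdrawal have their own table (15.6). Poor tolerability would be visible.
- Patients who stop for an AE have that event followed to resolution or stability, so they are not the worst-documented group.
- In the Phase 1 study 26 subjects received AK001 and none was discontinued for an AE (1.2). Early stops may be few.
- Exposure-adjusted rates are an analysis detail that section 15 leaves to the statistical analysis plan. Their absence from 15.6 is not a fault.

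All of this stands, and it narrows the point. It does not restore the missing data: no analysis can recover events that nobody was asked to record.

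**Conclusion.** The gap is real and rests on explicit text: new-onset AEs and SAEs after ET are not collected, while the protocol's own observation period runs 17 weeks past the last dose. What is exposed is additional or delayed events, which affects the preferred-term rows, serious TEAEs, maximum severity, and late life-threatening or fatal events that would count under 14.3. The any-TEAE row is largely unaffected for patients who stop because of an AE.

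The size cannot be fixed from the document. It depends on how many patients stop early and when, and it is near zero if stops are few. The 62% to 70% figure assumes first-order decay and ET on Day 14 after one dose. It shows that the patient is still exposed, not how many events would be missed. This is an inexpensive improvement to the safety data, not a flaw that undermines the trial.

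**What to change.** Separate stopping study drug from ending safety collection. In 9.2.8, 11.3.1 and 15.6, replace the Day 168 or ET end point with a statement that, for every dosed patient, including those who have had an ET visit, new AEs and SAEs are collected until Day 168 unless consent is withdrawn. Telephone contact is enough. Bring 12.1, 12.2 and the Day 168/ET column of Table 1 into line, since these define what ET ends.

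Use Day 168 as the single end date. Seventeen weeks after the last dose would end at Day 119 for a patient given one infusion and would leave follow-up unequal.

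The cost is amendment wording and a few telephone calls per early terminator; the protocol already uses safety calls after each infusion. No rule on dosing or on when drug is stopped needs to change.
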